3.3.2 Planned Study Duration

The expected time for study completion, from first subject in to last subject last visit is approximately 8 months.

4. STUDY ENROLLMENT AND WITHDRAWAL

4.1 Study Population

Subjects with known or suspected bacterial pneumonia being treated with SOC antibiotics and requiring mechanical ventilation who fulfill the following eligibility criteria will be enrolled.

4.2 Inclusion Criteria

Subjects who fulfill the following criteria will be included in the study:

1. Subject is male or female, 18-80 years (both inclusive) at the time written informed consent is obtained
2. Subject has provided written informed consent or informed consent has been provided by subject's legally authorized representative (Note: Country-specific rules and/or local state laws and local Ethics Committee approval for legally authorized representative informed consent will determine whether or not and how a subject unable to comprehend or sign the informed consent is allowed to be enrolled in the study)
3. Subject has a clinical diagnosis of bacterial pneumonia, documented or suspected, (even if later known that the subject does not have bacterial pneumonia, discontinuation of the study is not necessary)
4. Subject is hospitalized and receiving SOC antibiotic treatment for pneumonia
5. Subject is mechanically ventilated and is expected to remain mechanically ventilated for at least 48 hours (or 72 hours for subjects with severe renal impairment) after the first dose of cefiderocol
6. Subject has a life expectancy of at least 3 weeks from the Screening visit
7. Female meeting 1 of the following criteria:
 - a. Surgically sterile (has had a hysterectomy and/or bilateral oophorectomy, or a bilateral salpingectomy or tubal ligation for the purpose of contraception for at least 6 weeks with appropriate documentation of such surgery)
 - b. Postmenopausal (defined as older than 45 years of age with cessation of regular menstrual periods for at least 6 months and a history of a follicle-stimulating hormone level of > 40 mIU/mL, or amenorrhea for at least 12 months)
 - c. Of childbearing potential and using combined (estrogen and progestogen) or progestogen-only hormonal contraception associated with inhibition of ovulation (including oral, intravaginal, injectable, implantable, and transdermal contraceptives), or an intrauterine device (IUD) or intrauterine hormone-releasing system for the entire duration of the study
 - d. Of childbearing potential and practicing abstinence as a preferred and usual life style and/or agrees to continue practicing abstinence from Screening for the entire duration of the study

- e. Of childbearing potential and whose sole heterosexual partner has been successfully vasectomized and agrees to not have other heterosexual partners for the entire duration of the study

4.3 Exclusion Criteria

Subjects who meet any of the following criteria will be excluded from the study:

1. Subject has a chemical/aspiration pneumonia that does not require antibiotic treatment (including aspiration of gastric acid, inhalation injury). The term chemical pneumonia refers to the aspiration of substances that are toxic to the lower airways causing chemical burn and injuries in the airway.
2. Subject has a history of any moderate or severe hypersensitivity or allergic reaction to any β -lactam (Note: for β -lactams, a history of a mild rash followed by uneventful re-exposure is not a contraindication to enrollment)
3. Subject has extensive cystic lesion(s) or severe structural abnormality (eg, cystic fibrosis, emphysema, cystic lesions of sarcoidosis or tuberculosis, post obstructive pneumonia due to lung cancer, etc) of the lung that hinders recovery of bronchoalveolar lavage fluid (BALF)
4. Subject is receiving peritoneal dialysis.
5. Subject has severe renal impairment requiring hemodialysis (HD) or end-stage renal disease requiring HD with creatinine clearance (CrCl) < 15 mL/min
6. Subject is in refractory septic shock defined as persistent hypotension despite adequate fluid resuscitation or despite vasopressive therapy at Screening
7. Subject is a female who has a positive pregnancy test at Screening or who is lactating
8. Subject has received another investigational drug within 30 days prior to Screening
9. Subject has previously participated in this clinical study and has received at least 1 dose of cefiderocol
10. Subject has any condition or circumstance that, in the opinion of the investigator, would compromise the safety of the subject or the quality of the study data.

4.4 Screen Failures

Screen failures are defined as subjects who provide consent to participate in the study but are not subsequently dosed in the study. Minimal information will include informed consent date, baseline subject characteristics, all eligibility criteria not met, reasons for screen failure including reporting of AEs that lead to screen failure if applicable, and any SAEs and will be entered in the source documents and the eCRF.

Subjects who do not meet the criteria for participation in the study (screen failure) may be rescreened only once in this study. Rescreened subjects should be assigned a new subject number to distinguish it from the initial Screening.

4.5 Withdrawal of Subjects from the Study or Discontinuation from Study Drug

The investigator will make every reasonable attempt to complete the study for each study subject.

A subject may withdraw consent to participate in the study at any time, for any reason.

The investigator or subinvestigator may discontinue a subject from study drug at any time for any of the following reasons:

- A serious or intolerable AE occurs and the investigator or subinvestigator considers that the subject should discontinue study drug
- The subject recovers from the infection prior to the BAL procedure and inflammation no longer exists in the lung
- The subject is unable to undergo the BAL procedure or unable to provide an appropriate ELF sample
- The subject is proved to be ineligible for the study after the initiation of study
- The investigator or subinvestigator determines that the subject should be discontinued from the study drug based on the management and discontinuation criteria for abnormal liver function tests ([Appendix 2](#))
- The investigator or subinvestigator determines that the subject should be discontinued from study drug for any other reasons (eg, extubation)
- The study is prematurely terminated

In the event a subject withdraws consent or a subject is prematurely discontinued from study drug by the investigator or subinvestigator, the investigator or subinvestigator will promptly notify the sponsor. If a subject is prematurely discontinued from study drug by the investigator or subinvestigator, EOT (or early termination) procedures including physical examination, vital sign measurements, and clinical laboratory tests will be performed. The reporting of AEs will be obtained until the EOS visit, which occurs 7 days after the last dose of cefiderocol if there is no SAE. If an SAE is observed it must be reported to Safety and all SAEs, regardless of causality, will be followed until resolution, stabilization, the condition becomes chronic, or the subject is lost to follow-up. The investigator will make an effort to collect AEs for 7 days after the last dose of study drug.

If a subject withdraws or is discontinued from study or study drug, a replacement subject may be enrolled if deemed appropriate by the sponsor.

The date of withdrawal or discontinuation and reason for withdrawal or discontinuation will be entered in the source documents and the eCRF.

5. STUDY TREATMENT(S)

5.1 Description of Treatment(s)

5.1.1 Test Drug

Cefiderocol will be supplied in vials containing 1 g of cefiderocol as a white to light yellow cake or powder, manufactured by Shionogi & Co., Ltd. Each cefiderocol vial will be reconstituted in 0.9% saline (normal saline) to produce a clear solution and then extracted for further dilution in normal saline to prepare an infusion solution with a final concentration of at least 20 mg/mL for IV administration.

Each dose of cefiderocol will be prepared by the study pharmacist and labeled with appropriate information per local standards. A detailed procedure for preparation of the IV infusion solution will be provided in a separate pharmacy manual.

5.2 Treatments to be Administered

The dose of cefiderocol administered to each subject will be determined based on renal function as described in this section (see [Table 5-1](#)). Dosing recommendations for subjects with moderate or severe renal impairment and subjects with augmented renal clearance are provided. For all subjects serum creatinine levels should be checked once daily to determine whether dose adjustments of cefiderocol should be made.

Beginning on Day 1, subjects will be administered 2-g doses (or renally adjusted dose) of cefiderocol infused intravenously over 3 hours, q8h (or q6h for subjects with augmented renal function), for an expected minimum of 3 doses and up to a total of 6 doses in subjects with normal or augmented renal function and subjects with mild or moderate renal impairment, and for an expected minimum of 6 doses and up to a total of 9 doses in subjects with severe renal impairment. Cefiderocol dosing will be terminated once the BAL procedure has been performed and ELF samples, plasma PK samples, and urea samples have been collected for analyses at which time no further cefiderocol dosing will be permitted. After initiation of cefiderocol administration, doses of cefiderocol administered to each subject may be adjusted based on changes in renal function as assessed daily by CrCl (using the Cockcroft-Gault equation) and according to the dosing recommendations for subjects (see [Table 5-1](#)). Any dosing modifications based on the dosing recommendations will be agreed to by the investigator and documented. Please see the Renal Function and Dose Adjustment Log in the pharmacy manual.

Table 5-1 Dosing Recommendations of Cefiderocol Based on Renal Function

Creatinine Clearance	Dosage
Augmented renal function (CrCl \geq 120 mL/min) ^a	2 g, q6h, 3-hour infusion
Normal renal function (CrCl < 120 mL/min) ^a	2 g, q8h, 3-hour infusion
Mild renal impairment (CrCl 60 to < 90 mL/min) ^a	2 g, q8h, 3-hour infusion
Moderate renal impairment (CrCl 30 to < 60 mL/min) ^a	1.5 g, q8h, 3-hour infusion
Severe renal impairment (CrCl 15 to < 30 mL/min) ^a	1 g, q8h, 3-hour infusion

CrCl = creatinine clearance; q6h = every 6 hours; q8h = every 8 hours

a Creatinine clearance will be calculated by Cockcroft-Gault equation at Screening.

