1. Subject has a chemical/aspiration pneumonia that does not require antibiotic treatment (including aspiration of gastric acid, inhalation injury). The term chemical pneumonia refers to the aspiration of substances that are toxic to the lower airways causing chemical burn and injuries in the airway.
2. Subject has a history of any moderate or severe hypersensitivity or allergic reaction to any β -lactam (Note: for β -lactams, a history of a mild rash followed by

- uneventful re-exposure is not a contraindication to enrollment)
3. Subject has extensive cystic lesion(s) or severe structural abnormality (eg, cystic fibrosis, emphysema, cystic lesions of sarcoidosis or tuberculosis, post obstructive pneumonia due to lung cancer, etc) of the lung that hinders recovery of bronchoalveolar lavage fluid (BALF)
 4. Subject is receiving peritoneal dialysis
 5. Subject has severe renal impairment requiring hemodialysis (HD) or end-stage renal disease requiring HD with creatinine clearance (CrCl) < 15 mL/min
 6. Subject is in refractory septic shock defined as persistent hypotension despite adequate fluid resuscitation or despite vasopressive therapy at Screening
 7. Subject is a female who has a positive pregnancy test at Screening or who is lactating
 8. Subject has received another investigational drug within 30 days prior to Screening
 9. Subject has previously participated in this clinical study and has received at least 1 dose of cefiderocol
 10. Subject has any condition or circumstance that, in the opinion of the investigator, would compromise the safety of the subject or the quality of the study data

Test Drug, Dose, and Mode of Administration:

Cefiderocol, 2 g, is to be administered intravenously q8h as a 3-hour infusion in subjects with normal, mild, moderate or severe renal function (or q6h if subject has augmented renal function) in addition to the subject's treatment with SOC. Dose adjustment for renal function is required, and the dosing recommendations are presented in the protocol, [Section 3.1](#).

Control Drug, Dose, and Mode of Administration:

Not applicable

Duration of Treatment:

The treatment duration for cefiderocol is anticipated to be 3 to 4 days depending on the subject's renal function.

Prohibited Concomitant Therapy:

Not applicable

Efficacy Assessments:

Not applicable

Pharmacokinetic Assessments:

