5.4 Method of Assigning Subjects to Treatment Groups

This is a single-arm study and each qualified subject with normal or augmented renal function or mild or moderate renal impairment will receive administration of an expected minimum of 3 doses and up to a total of 6 doses while subjects with severe renal impairment will receive administration of an expected minimum of 6 doses and up to a total of 9 doses.

If rescreening of a subject takes place, the rescreening subject number will be 100 more than the original (eg, Subject Number 001 will be replaced by Subject Number 101).

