 - g Data from chest X-rays performed as part of routine patient care will be collected at Screening and throughout the study in accordance with routine patient care; any chest X-ray taken within 48 hours of randomization can be considered as Screening (or baseline) chest X-ray. A computed tomography scan can be a substitute of chest X-ray if taken according to local standard of care.
 - h Data from clinical laboratory tests performed as part of routine patient care will be collected at Screening and from the first dose of cefiderocol, during administration of cefiderocol, and until the last dose of cefiderocol. Clinical laboratory tests during the treatment period will be symptom-driven and at the investigator's discretion. If a microbiology test has been performed to confirm the clinical diagnosis (before or during Screening), the results should be recorded in the source documents and the eCRF.
 - i Creatinine clearance must be calculated at Screening and daily during treatment period to determine cefiderocol dose.
 - j Female subjects of childbearing potential only.
 - k EOT assessments will occur within 24 hours after administration of the last dose of cefiderocol or at early termination.
 - l If an SAE is observed it must be reported to Safety and all SAEs, regardless of causality, will be followed until resolution, stabilization, the condition becomes chronic, or the subject is lost to follow-up. The investigator will make an effort to collect AEs for 7 days after the last dose of study drug.
 - m Multiple doses of cefiderocol administered as an intravenous infusion over 3 hours, every 8 hours (q8h), or every 6 hours (q6h) if augmented renal function, beginning on Day 1 and continuing for an expected minimum of 3 doses and up to a total of 6 doses in subjects with normal or augmented renal function and subjects with mild or moderate renal impairment and for an expected minimum of 6 doses and up to a total of 9 doses in subjects with severe renal impairment. Dose adjustments will be made based on renal function according to dosing recommendations per protocol. Dosing scheme of q6h is not illustrated in the Schedule of Events Table as it is expected to a rare situation.

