3.2.2. Exclusion Criteria

Subjects who meet any of the following criteria will be excluded from the study:

1. Subject has a chemical/aspiration pneumonia that does not require antibiotic treatment (including aspiration of gastric acid, inhalation injury). The term chemical pneumonia refers to the aspiration of substances that are toxic to the lower airways causing chemical burn and injuries in the airway.
2. Subject has a history of any moderate or severe hypersensitivity or allergic reaction to any β -lactam (Note: for β -lactams, a history of a mild rash followed by uneventful re-exposure is not a contraindication to enrollment)
3. Subject has extensive cystic lesion(s) or severe structural abnormality (eg, cystic fibrosis, emphysema, cystic lesions of sarcoidosis or tuberculosis, post obstructive pneumonia due to lung cancer, etc) of the lung that hinders recovery of bronchoalveolar lavage fluid (BALF)
4. Subject is receiving peritoneal dialysis
5. Subject has severe renal impairment requiring hemodialysis (HD) or end-stage renal disease requiring HD with CrCl < 15 mL/min
6. Subject is in refractory septic shock defined as persistent hypotension despite adequate fluid resuscitation or despite vasopressive therapy at Screening
7. Subject is a female who has a positive pregnancy test at Screening or who is lactating
8. Subject has received another investigational drug within 30 days prior to Screening
9. Subject has previously participated in this clinical study and has received at least 1 dose of cefiderocol
10. Subject has any condition or circumstance that, in the opinion of the investigator, would compromise the safety of the subject or the quality of the study data.

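### The Normal row of the dosing tables has no lower CrCl bound; read as intended (90 to < 120), it leaves CrCl < 15 mL/min without hemodialysis with no dose or stop rule in the protocol or SAP

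*Protocol*

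**What the plan says.** **Dosing tables.** Protocol Tables 3-1 and 5-1 and SAP Tables 1 and 2 give the same five bands. Mild, Moderate and Severe each carry a lower and an upper limit, and the lowest band stops at 15 mL/min. The Normal row reads "Normal renal function (CrCl < 120 mL/min" and has an upper limit only.

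**Renal adjustment.** The synopsis states "Dose adjustment for renal function is required" and points to Section 3.1 for the doses. Protocol 5.2 says that "doses of cefiderocol administered to each subject may be adjusted based on changes in renal function as assessed daily by CrCl", using Table 5-1. Footnote i of Protocol Appendix 1 adds: "Creatinine clearance must be calculated at Screening and daily during treatment period to determine cefiderocol dose". Protocol 5.2 also directs staff to a document outside the protocol: "Please see the Renal Function and Dose Adjustment Log in the pharmacy manual".

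**Eligibility.** Exclusion 5 in the synopsis and Protocol 4.3 reads "Subject has severe renal impairment requiring hemodialysis (HD) or end-stage renal disease requiring HD with creatinine clearance (CrCl) < 15 mL/min". SAP 3.2.2 has the same criterion: "Subject has severe renal impairment requiring hemodialysis (HD) or end-stage renal disease requiring HD with CrCl < 15 mL/min". Exclusion 4 covers peritoneal dialysis. Exclusion 10 leaves other conditions to the investigator's opinion.

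**Stopping.** Protocol 4.5 refers to specific liver-test criteria and to a general discretionary reason. It lists no renal criterion.

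**The concern.** These tables set the dose at entry, and the daily CrCl check refers back to them. According to Protocol 1.5.1, about 90% of the drug is excreted unchanged in urine, and Protocol 5.3 says that renal function must guide the dose. A band with an open lower end in such a table gives two doses for some subjects. It also leaves it unclear what the plan intends for the subjects with the least renal function.

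What is at stake is the safety of a subject whose CrCl is below 15 without hemodialysis, either at screening or after a fall during dosing. An investigator working from the protocol and SAP would have to choose between a row labelled Normal that cannot have been meant for that subject and no instruction at all.

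**Working it through.** No sample-size or power figure bears on this point. The check maps each CrCl range to the printed rows, then repeats the mapping with the evident lower limit of 90 for Normal. That limit is inferred from the row label and from the Mild band ending at < 90.

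| CrCl (mL/min) | Rows matched as printed | Row matched with Normal = 90 to < 120 |
|---|---|---|
| ≥ 120 | Augmented, 2 g q6h | Augmented |
| 90 to < 120 | Normal, 2 g q8h | Normal |
| 60 to < 90 | Normal, 2 g q8h; Mild, 2 g q8h | Mild |
| 30 to < 60 | Normal, 2 g q8h; Moderate, 1.5 g q8h | Moderate |
| 15 to < 30 | Normal, 2 g q8h; Severe, 1 g q8h | Severe |
| < 15 | Normal, 2 g q8h | none |

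**Overlap, as printed.** Two rows apply from 15 to < 90. The doses agree at 60 to < 90 and conflict at 15 to < 60. In the three tables that also give the number of doses before BAL (Protocol Table 3-1, SAP Tables 1 and 2), that range conflicts too at 15 to < 30: 3-6 under Normal and 6-9 under Severe.

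**Gap, as intended.** With the lower limit at 90, every value of 15 or more falls in exactly one row, and values below 15 fall in none. The overlap and the gap therefore belong to different readings. As printed, CrCl < 15 does have a dose, and it is the full one. As intended, it has none. Restoring the bound alone does not settle what happens below 15.

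**Does eligibility close the gap?** Both limbs of exclusion 5 depend on requiring hemodialysis, so CrCl < 15 alone does not meet it. Exclusion 4 does not apply without peritoneal dialysis. Protocol 5.4 divides subjects into "each qualified subject with normal or augmented renal function or mild or moderate renal impairment" and those with severe impairment. This suggests that nobody below 15 was meant to qualify, but no criterion says so.

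**Does the on-treatment text close it?** The study admits subjects down to CrCl 15, and severe impairment means 6 to 9 doses. A subject who enters just above 15 and then worsens leaves the bottom row. The daily check refers back to the same table. The reason in Protocol 4.5 for a subject found ineligible does not clearly apply, because no stated criterion has been breached.

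**Where the threshold lies.** Protocol 7.6.4.1.2 gives the Cockcroft-Gault formula. Solved for serum creatinine at CrCl = 15:

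creatinine (mg/dL) = weight × (140 − age) × (0.85 if female) / (72 × 15), where 72 × 15 = 1080.

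- Woman, 80 years, 50 kg: 50 × 60 × 0.85 / 1080 = 2.36
- Man, 70 years, 70 kg: 70 × 70 / 1080 = 4.54
- Man, 18 years, 100 kg: 100 × 122 / 1080 = 11.3

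The ages lie within inclusion criterion 1. The ages chosen and the weights are illustrative assumptions. Whether such a subject requires hemodialysis is a clinical decision that the formula does not settle.

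**The case against.** The strongest reply is that nobody would be misdosed.

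- **Context resolves the overlap.** Each impairment row is labelled and bounded, and the synopsis and Protocol 5.3 require renal adjustment. An investigator with a subject at CrCl 25 would use the Severe row. This largely stands. It is not a complete repair: the synopsis names 2 g q8h for normal through severe function before requiring adjustment, then points to the table with the open row.
- **Judgement is built in.** The tables are recommendations, Protocol 3.1 has the investigator determine the dose, and exclusion 10 and Protocol 4.5 allow a subject to be kept out or stopped. This stands as a safeguard. It still supplies no dose or threshold below 15.
- **Exposure is short and watched.** At q8h, the sixth dose starts at hour 40 and the ninth at hour 64. Dosing ends once the BAL and related samples are taken, and CrCl is calculated daily. Under Protocol 7.6.5.6, a laboratory result that changes dosing is treated as clinically significant and recorded as an adverse event. This limits the reach of the gap but does not close it.
- **The rule may exist elsewhere.** The pharmacy manual contains a log named for this purpose. This stands, and it limits the claim to what the protocol and SAP say.
- **The SAP tables dose nobody.** This is correct. They are copies that need aligning, not a second source of risk.

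**Conclusion.** The concern holds in a limited form. The missing lower bound is certain on the text: it recurs in four separate tables whose other ranges came through intact. Its overlap at 15 to < 90 is a drafting error with little likely consequence. The safety point is CrCl < 15 without hemodialysis. On the intended reading, the protocol and SAP give such a subject no dose, no exclusion and no stop rule. The reach is low in a study of up to about 18 subjects. Confidence in the gap is moderate, because it depends on the intended reading and on a pharmacy manual that was not available.

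A reader might infer three stronger things that the documents do not support:

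- **That subjects below 15 would actually receive 2 g q8h, at some multiple of normal exposure.** The literal table says 2 g, but the row label and the adjustment text make that unlikely in practice. Any exposure multiple would also need clearance assumptions that the plan does not give.
- **That the study has no renal stop rule at all.** Only its absence from these two documents is shown.
- **That the PK results are compromised.** The planned ELF and ratio summaries are by nominal sampling time and do not depend on the CrCl bands.

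**What to change.** 1. Set the Normal row to CrCl 90 to < 120 mL/min in Protocol Tables 3-1 and 5-1, and align SAP Tables 1 and 2.
2. Amend exclusion 5 in the synopsis and Protocol 4.3 to exclude CrCl < 15 mL/min whether or not hemodialysis is required, and align SAP 3.2.2.
3. State in Protocol 5.2 and 4.5 that study drug stops if CrCl falls below 15 mL/min on treatment, unless the sponsor specifies a dose for that range. If the pharmacy manual already has a rule, repeat it in Protocol 5.2.

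The text changes are one bound in four tables, one criterion in three places, and a sentence in each of two sections. A protocol amendment is needed, with written IRB approval before implementation (Protocol 10.10). A very small number of subjects would be excluded or stopped. No PK analysis changes.
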